11.5. Left Ventricular Ejection Fraction (LVEF) Assessment

LVEF assessment values by visit and change from baseline will be summarized using descriptive statistics. Similarly, maximum and minimum post-baseline values and corresponding change from baseline values will be summarized using descriptive statistics.

Shift from baseline to worst post-baseline in the overall LVEF interpretation ('Normal', 'Abnormal, not clinically significant' and 'Abnormal, clinically significant') will be displayed in cross-tabulations by treatment arm and dose cohort.

A summary table of severity grade for LVEF will be provided using levels of "Ejection fraction decreased" from NIC CTCAE (Version 4.03):

- Grade 2 = Resting ejection fraction: 50 - 40%; 10 - 19% drop from baseline.
- Grade 3 = Resting ejection fraction: 39 - 20%; >20% drop from baseline.
- Grade 4 = Resting ejection fraction: <20%.

Moreover, descriptive summary statistics for baseline and worst post baseline LVEF will be provided by dose cohort, overall and treatment arm.

A listing of LVEF by treatment arm and dose cohort will be provided as well.

11.6. Other Safety Assessments

Data collected for other safety assessments including pregnancy status, ophthalmologic examination, tumor lysis and tumor flare will be listed by treatment arm and dose cohort.

Spleen and liver physical examination assessments ('Normal' and 'Abnormal') for Safety population at each visit will be summarized using frequency count by dose cohort, overall and treatment arm. Data collected for physical exam for liver and spleen will be also listed.

12.1. PK and Exposure Response Analyses

During the Dose Escalation phase, intensive PK sampling will be performed in a minimum of 3 subjects in the first cycle in Arm A (Cycle 1, Days 1 and 15). PK parameters will be estimated based on the intensive PK population. Actual sampling times will be used in the calculations of PK parameters by using the non-compartmental analysis (NCA) method. Drug concentrations reported by the bioanalytical laboratory as Below the Quantification Limit (BQL) will be shown as BQL in the data listings. If >50% of results for a given timepoint and dose level, are reported as below the Low Limit of Quantification (LLOQ: 1.0 ng/mL), the mean, median and geometric mean are reported as LLOQ. In these scenarios, the other descriptive statistics are not calculated. Missing concentrations will be treated in PK calculations as if they were never drawn. If a concentration is missing (e.g., because no sample was taken, there was no valid result [including concentrations after dosing which are BQL], there was no detectable peak or the sample was lost), the concentration will not be imputed (i.e., it will remain missing). Every effort will be made to include all concentration data in the analysis. In the event that an actual sample collection time is missing for a certain time point, the planned time may be used for this time point instead.

Pharmacokinetic Plasma Concentrations:

CC-122 plasma concentrations from intensive sampling will be summarized by actual dose level, visit, and nominal time points. In general, geometric mean and the geometric CV (%) will be derived from non-zero concentration values. These results will be tabulated by dose cohort and treatment arms.

CV (%) is calculated as follows: $CV\% = \frac{StdDev}{mean} \times 100\ldots$

Geometric CV (%) is calculated as follows: $CV(\%) = 100 \times \sqrt{(\exp(\sigma^2) - 1)}$, where σ^2 denotes the variance of the log-transformed values.

The following figures will be provided by dose cohort using intensive PK population:

- Individual subject's concentration (linear scale and semi-logarithmic scale) over time spaghetti plot;
- Mean and \pm Std Dev of concentration (linear scale and semi-logarithmic scale) over time plot;

Note: Mean of 1 ng/mL at timepoint 0 will be imputed when more than 50% of values are below LLOQ.

Summary for Ibrutinib plasma concentration will not be performed due to limit data collected.

Pharmacokinetic Parameters:

For Arm A (CC-122 single agent), intensive PK samples collected are still very limited in time-points and limited in valid concentration values. For Arm B (CC-122 in combination with ibrutinib) and Arm C (CC-122 in combination with obinutuzumab), only sparse PK samples were collected. Therefore, the analyses on the PK parameters stated in protocol (i.e. C_{max} , T_{max} , AUC_t , etc.) will not be performed. Please see the details in Section 15 changes to the statistical analyses section of the protocol.

Following by-subject listings will be provided for all Enrolled population:

- PK blood sampling
- Individual CC-122 plasma concentration for scheduled timepoints
- Individual Ibrutinib plasma concentration for scheduled timepoints

[REDACTED]

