5.2.4. Pharmacokinetic (PK) Population

PK population - all subjects who have at least one measurable CC-122 and/or ibrutinib concentration datum. Subjects will be summarized under the actual dose level corresponding to the PK sample collection.

Intensive PK Population is defined as all subjects who have at least one measurable CC-122 concentration datum from intensive sampling. Intensive PK population will be used to support summaries for CC-122 PK concentrations and parameters from the intensive sampling.

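### SAP 12.1 plots 1 ng/mL before the first CC-122 dose and its rules for values below quantification push the concentration summaries upward (minor)

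*SAP*

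**What the plan says.** SAP 12.1 gives the limit as "Low Limit of Quantification (LLOQ: 1.0 ng/mL") and handles values below it (BQL) in three ways.

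- **More than half BQL.** The condition begins "If >50% of results for a given timepoint and dose level, are reported as below" the LLOQ. In that case "the mean, median and geometric mean are reported as LLOQ", and no other descriptive statistics are calculated.
- **Missing values.** The examples of a missing concentration include cases where "there was no valid result [including concentrations after dosing which are BQL". For all of them, "the concentration will not be imputed (i.e., it will remain missing").
- **Mean plots.** A note to the concentration-time figures, which are drawn on linear and semi-logarithmic scales, says "Mean of 1 ng/mL at timepoint 0 will be imputed when more than 50% of values are below LLOQ".

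The same section says that "geometric mean and the geometric CV (%) will be derived from non-zero concentration values", although no visible sentence sets any value to zero. Listings show BQL results as BQL. Intensive sampling is planned in at least 3 Arm A subjects on Cycle 1 Days 1 and 15. SAP 5.2.4 defines the intensive PK population as "all subjects who have at least one measurable CC-122 concentration datum from intensive sampling".

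**The concern.** A BQL result is a known low value, between 0 and 1.0 ng/mL; it is not an absent one. Leaving it out, or replacing the centre of the distribution by the upper end of that interval, tends to move the summary upward. In Arm A the first CC-122 dose is on Cycle 1 Day 1 (SAP 4.1.1 and 8.1), so the time 0 sample on that day precedes all drug. A plotted mean of 1 ng/mL there shows exposure that cannot exist.

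What is at stake is limited but real. CC-122 plasma concentration is a secondary endpoint (Protocol 3.2). SAP 12.1 and 15 drop the PK parameter analyses, and Arms B and C have only sparse samples. The intensive-sampling tables and mean plots are therefore the main CC-122 PK summary that remains.

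**Working it through.** **Inputs from the documents.** LLOQ 1.0 ng/mL; switch at more than 50% BQL; value above the switch 1.0; post-dose BQL left missing (all SAP 12.1). Minimum of 3 subjects (SAP 12.1). First Arm A dose on Cycle 1 Day 1 (SAP 8.1).

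**Assumed, because the documents give no concentrations.** Log-normal values with geometric mean (GM) 1.0, 1.2 or 1.5 ng/mL; CV 30%, 50% or 70%; n = 3 or 6.

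**1. The plan's own figure.** Cycle 1 Day 1, time 0, n = 3, all BQL: the share is 3/3 = 100%, which exceeds 50%, so the plotted mean is 1.0 ng/mL. This reproduces the SAP's value. The true value is 0.

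**2. At or below 50% BQL.** Let f be the share BQL, m_q the mean of the quantifiable values and m_b the unknown true mean of the BQL values (below 1.0). The plan reports m_q. The mean of all samples is (1 − f)m_q + f·m_b. The difference is f(m_q − m_b), which is positive whenever f > 0.

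- BQL, 1.2, 1.5: reported 2.7/2 = 1.35. The full mean lies between 2.7/3 = 0.90 and 3.7/3 = 1.23.
- Three BQL with 1.2, 1.5, 2.0: reported 4.7/3 = 1.57. The full mean lies between 4.7/6 = 0.78 and 7.7/6 = 1.28.

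**3. Above 50% BQL.** More than half the values are below 1.0, so the sample median is below 1.0 and the reported 1.0 is always too high. The mean can go either way:

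- All BQL: reported 1.00, true value anywhere from 0 to just under 1.00.
- Two BQL and 3.5: reported 1.00, true value between 3.5/3 = 1.17 and 5.5/3 = 1.83, so the report is too low.

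With n = 3, moving from one BQL value to two switches the statistic from the mean of the quantifiable values to the constant 1.0.

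**4. Both branches together.** With σ² = ln(1 + CV²), the true mean is GM·exp(σ²/2). I applied the rule to 400,000 simulated samples per setting. The last column sets every BQL value to LLOQ/2 = 0.5, for comparison.

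| CV | GM | SAP rule, n = 3 | SAP rule, n = 6 | LLOQ/2 |
|---|---|---|---|---|
| 30% | 1.0 | +9.4% | +13.7% | −14.5% |
| 30% | 1.2 | +6.2% | +10.3% | −7.4% |
| 30% | 1.5 | +3.1% | +4.0% | −2.1% |
| 50% | 1.0 | +12.9% | +20.2% | −9.5% |
| 50% | 1.2 | +9.8% | +17.9% | −6.6% |
| 50% | 1.5 | +7.5% | +12.1% | −3.4% |
| 70% | 1.0 | +14.5% | +24.7% | −6.0% |
| 70% | 1.2 | +12.1% | +23.3% | −4.7% |
| 70% | 1.5 | +10.2% | +18.6% | −3.1% |

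The average error of the arithmetic mean under the SAP rule is upward throughout, about 3% to 25%. In individual samples the reported mean fell below the sample's own mean in up to 16% of cases, all of them in the branch above 50%.

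**The case against.** **The text may be narrower than it looks.** The missing-value sentences follow a remark about PK calculations, and the non-compartmental calculations have been cancelled. BQL values count as results for the 50% threshold, the section promises every effort to include all data, and the reference to non-zero values hints that some zeros are kept. This stands in part. However, the sentence on not imputing is worded generally, and no other visible rule covers 50% BQL or fewer. On the narrow reading the summary has no rule there, which also needs a wording change. The time 0 and above-50% rules are not ambiguous.

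**The consequence is small.** This stands. The outputs are descriptive, Phase 2 is cancelled, no safety or efficacy result uses these means, and listings and individual profiles remain available to the reader.

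**Stronger readings that the documents do not support:**

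- *A much larger inflation.* Modelling only the dropping rule, at GM 1.0 and CV 70% the quantifiable-only mean is 1.80 against a true 1.22, or +47%. But half the values are then BQL, so the above-50% branch applies in about half of samples with n = 3 and a third with n = 6. The combined figures are +14.5% and +24.7%.
- *Every reported mean is too high.* The two-BQL-and-3.5 example shows otherwise.
- *The bias sits in the low-dose starters and late samples and flattens the dose relation.* The documents give no concentrations or BQL counts, and no PK sampling schedule is visible, so this would be an assumption.
- *Every time 0 value should be zero.* Day 15 predose follows earlier dosing and may truly be above zero.
- *The intensive PK population should be widened to all-BQL subjects.* That would put them outside the parent PK population, which also requires a measurable concentration (Protocol 10.2, SAP 5.2.4).

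**Conclusion.** The point holds, at minor severity. Two results need no distributional assumption: the Cycle 1 Day 1 predose mean is plotted as 1 ng/mL against a true 0 whenever more than half the values are BQL (taking time 0 as predose), and above 50% BQL the reported median is always too high. At or below 50%, read as written, the reported mean is also always too high when any post-dose value is BQL. The overall size, about 3% to 25% for the arithmetic mean, rests on the assumed log-normal distribution, GM, CV and n. The actual number of BQL samples is unknown. The effect is confined to CC-122 concentration tables and mean plots.

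**What to change.** In SAP 12.1:

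1. Set Cycle 1 Day 1 predose BQL values to 0 in tables and plots, and remove the 1 ng/mL imputation for that point. Omit the point on the semi-log plot and do not calculate a geometric mean there.
2. When more than 50% are BQL at any other time point, report the centre as BQL (<1.0), not as 1.0.
3. Show n and n BQL at every time point and dose level.
4. At or below 50% BQL, keep post-dose BQL results in the summary under one stated substitution, for example LLOQ/2, labelled as a convention. State its own error: applied to all samples in the grid above it lowers the mean by about 2% to 15%. With at most half the values BQL, it can shift any one sample mean by no more than 0.5 × 0.5 = 0.25 ng/mL in either direction.
5. Leave the intensive PK population as defined, and report the number of sampled subjects whose values are all BQL.

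The cost is a few sentences of SAP text and a change to one derivation. Some reported means will be lower, and time points above 50% BQL will have no numeric centre to plot.

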14. INTERIM ANALYSIS

As of Protocol Amendment 7, Phase 2 Expansion Phase will not proceed. The Interim analysis originally planned for the futility analysis of the expansion cohorts will not be conducted.

15. CHANGES TO THE STATISTICAL ANALYSES SECTION OF THE PROTOCOL

- As of Protocol Amendment 7, Phase 2 Expansion Phase will not proceed. Any analysis on the endpoints related to expansion phase, as well as the futility analysis of the expansion cohorts and interim analysis, will not be conducted.
- As intensive PK samples collected are still very limited in timepoints and limited in valid concentration values, analyses on PK (pharmacokinetic) parameter will not be conducted. As a result, the outputs for secondary endpoint “CC-122 pharmacokinetic parameters when administered in combination with Ibrutinib” will not be included in the final CSR package. The analysis on secondary endpoint “Ibrutinib plasma concentrations and/or pharmacokinetic parameters when administered in combination with CC-122” will not be conducted either. However, a by-subject listing for Ibrutinib plasma concentrations for the subjects who received Ibrutinib will be provided.
- In addition, analyses on biomarkers will not be performed and included in the final CSR package. Results might be reported separately. Similarly, the analysis on exploratory endpoint “Response rate, duration of response, and progression free survival in subtypes defined by biomarkers” will not be performed as well.

A series of 15 horizontal black bars of varying lengths, decreasing from left to right. The bars are positioned against a white background. The first bar is the longest, and each subsequent bar is progressively shorter, creating a visual gradient from left to right.

17. APPENDICES

17.1. Dose Escalation Rules

Table 8: Intrasubject Dose Escalation and Fixed-Doses Cohort Escalation Rules

Arm	No. of subjects recruited	Number of subjects that meet the criteria for DLT	NTD
Arm A ^[a]	20	> 20 %	
Arm B ^[b]	3+3	≥2	Yes
Arm C ^[b]	3+3	≥2	Yes

Notes:

^[a] Intrasubject escalation.

^[b] Fixed-doses cohort escalation.

17.2. Handling of Dates

Dates will be stored as numeric variables in the SAS analysis files and reported in DDMMYY format (i.e., the Date9. datetime format in SAS). Dates in the clinical database are classified into the categories of procedure dates, log dates, milestone dates, outcome dates, and special dates.

- **Procedure Dates** are the dates on which given protocol-specified procedure are performed. They include the dates of laboratory testing, physical examinations, tumor scans, etc. They should be present whenever data for a protocol-specified procedure are present and should only be missing when a procedure are marked as NOT DONE in the database. Procedure dates will not be imputed.
- **Log Dates** are dates recorded in CRF data logs. Specifically, they are the start and end dates for AEs and concomitant medications/procedures. They should not be missing unless an event or medication is marked as ongoing in the database. Otherwise, incomplete log dates will be imputed according to the rules in Appendix 17.4. However, in listings, log dates will be shown as recorded without imputation.
- **Milestone Dates** are dates of protocol milestones such as randomization, study drug start date, study drug termination date, study closure date, etc. They should not be missing if the milestone occurs for a subject. They will not be imputed.
- **Outcome Dates** are dates corresponding to study endpoints such as survival, progression, etc. In most cases they are derived either from a milestone (e.g., the survival date is derived from the death date), or a procedure date (e.g., the progression date is derived from the date of the tumor scan that was used to determine progression). They may be subject to endpoint-specific censoring rules if the outcome did not occur but are not otherwise subject to imputation.
- **Special Dates** cannot be classified in any of the above categories and they include the date of birth. They may be subject to variable-specific censoring and imputation rules.

Dates recorded in comment fields will not be imputed or reported in any specific format.

17.2.1. Calculation Using Dates

Calculations using dates (e.g., subject's age or relative day after the first dose of any study drug) will adhere to the following conventions.

Study days after the start day of study drug (referred as DSTART) will be calculated as the difference between the date of interest and the first date of dosing of study drug plus 1 day. The generalized calculation algorithm for relative day is the following:

If TARGET DATE \geq DSTART then STUDY DAY = (TARGET DATE – DSTART) + 1;

Else use STUDY DAY = TARGET DATE – DSTART.

Note that Study Day 1 is the first day of treatment of study drug (i.e. the earliest date between CC-122, ibrutinib and obinutuzumab). Negative study days are reflective of observations obtained during the baseline/screening period. Note: Partial dates for the first study drug are not imputed in general. All effort should be made to avoid incomplete study drug start dates.

Age (expressed in days) is calculated: AGE = CONSENT – DATE of BIRTH + 1. In practice, age will be transformed into years by dividing the difference by 365.25 days, then truncating. Preference is for using calculated age from clinical database. When not available, calculated age from CRF or Interactive Voice Response System (IVRS) may be used.

Partial birth date: impute missing day as 15th of the month; impute missing month as July; set missing age for missing year.

Intervals that are presented in weeks will be transformed from days to weeks by using (without truncation) the following conversion formula: WEEKS = DAYS / 7

Intervals that are presented in months will be transformed from days to months by using (without truncation) the following conversion formula: MONTHS = DAYS / 30.4375

17.2.2. Calculation of Cycles

Study Treatment Cycles

The start date of each cycle is defined as the first day when the subject receives CC-122, ibrutinib or obinutuzumab (non-zero dose) in that cycle. After the start dates are determined, the end date of each cycle is defined as (start date of subsequent cycle-1). The end date of the last cycle will be the last dose date for any study drug, the last dose date of CC-122+2 days or the Day 28 from the start of the last cycle, whichever is later. Any doses of study drug with start/stop dates on or after Day 1 of Cycle 1 but before Day 1 of Cycle 2 will be counted as taken in the Cycle 1. Any doses of study drug taken on or after Day 1 of Cycle 2 but before Day 1 of Cycle 3 will be counted as taken in the Cycle 2, and so forth. Any doses of study drug taken on or after the first day of the last cycle will be counted as taken in the last cycle.

After last cycle in treatment phase, cycles might be defined with 28-days intervals as necessary.

CC-122 Cycles

CC-122 cycle is also defined: CC-122 cycle starts after first CC-122 dose (C1D1 for Arm A, C2D1 for Arm B and C1D9 for Arm C) and each CC-122 cycle lasts 28 days.

17.3. Baseline, Repeated Measurements, and End of Trial

The general conventions for handling baseline, repeated measurements, and End of Trial (EOT) are provided below:

- Baseline for any clinical laboratory test, efficacy endpoints and vital sign is defined as the last value of a specific endpoint measured before the first dose of the IP.

- Baseline values for biomarkers will be the average of non-missing values collected at screening and the last value before first dose of the IP, if both samples are collected. Otherwise, either the values collected at screening or the last value of a specific endpoint measured before the first dose of the IP, whichever is collected, will be used as the baseline. Other pre-dose samples from on-treatment visits after the first dose of the IP will not be used to impute baseline value.
- Central laboratory values will be used; local laboratories will be used only if there is not any central laboratory by first dose date. When there are multiple values for any laboratory test (clinical and biomarker) or vital sign collected at the same visit, the one with last/latest assessment time stamp will be used for data analysis.
- End of trial assessment for a particular endpoint is defined as the last non-missing post-baseline assessment during the study period.
- Adequate efficacy assessment encompasses protocol defined assessments of tumor lesions (lymph nodes, spleen, and liver), peripheral blood test, bone marrow assessment when indicated, and clinical assessment.

17.4. Date Imputation Guideline

This subsection gives guideline on imputation of complete or partial missing AEs, or Concomitant medications start and/or stop dates.

Incomplete Start Date:

Missing day and month

- If the year is the same as the year of the first dosing date, then the day and month of the first dosing date will be assigned to the missing fields.
- If the year is prior to the year of first dosing date, then December 31 will be assigned to the missing fields.
- If the year is after the year of first dosing, then January 1 will be assigned to the missing fields.

Missing day only

- If the month and year are the same as the year and month of first dosing date, then the first dosing date will be assigned to the missing day.
- If either the year of the partial date is before the year of the first dosing date or the years of the partial date and the first dosing date are the same but the month of partial date is before the month of the first dosing date, then the last day of the month will be assigned to the missing day.
- If either the year of the partial date is after the year of the first dosing date or the years of the partial date and the first dose date are the same but the month of partial date is after the month of the first dosing date, then the first day of the month will be assigned to the missing day.
- If the stop date is not missing, and the imputed start date is after the stop date, the start date will be imputed by the stop date.

Missing day, month, and year

- No imputation is needed, the corresponding AE will be included as TEAE.

Incomplete Stop Date: If the imputed stop date is before the start date, then the imputed stop date will be equal to the start date.

Missing day and month

- If the year of the incomplete stop date is the same as the year of the last dosing date, then the day and month of the last dosing date will be assigned to the missing fields.
- If the year of the incomplete stop date is prior to the year of the last dosing date or prior to the year of the first dosing date, then December 31 will be assigned to the missing fields.
- If the year of the incomplete stop date is prior to the year of the last dosing date but is the same as the year of the first dosing date, then the first dosing date will be assigned to the missing date.
- If the year of the incomplete stop date is after the year of the last dosing date, then January 1 will be assigned to the missing fields.

Missing day only

- If the month and year of the incomplete stop date are the same as the month and year of the last dosing date, then the day of the last dosing date will be assigned to the missing day.
- If either the year of the partial date is not equal to the year of the last dosing date or the years of the partial date and the last dosing date are the same but the month of partial date is not equal to the month of the last dosing date, then the last day of the month will be assigned to the missing day.

10. **What is the primary purpose of the *Journal of Clinical Endocrinology and Metabolism*?**

10 of 10

[figure not shown]
■ **1** **2** **3** **4** **5** **6** **7** **8** **9** **10** **11** **12** **13** **14** **15** **16** **17** **18** **19** **20** **21** **22** **23** **24** **25** **26** **27** **28** **29** **30** **31** **32** **33** **34** **35** **36** **37** **38** **39** **40** **41** **42** **43** **44** **45** **46** **47** **48** **49** **50** **51** **52** **53** **54** **55** **56** **57** **58** **59** **60** **61** **62** **63** **64** **65** **66** **67** **68** **69** **70** **71** **72** **73** **74** **75** **76** **77** **78** **79** **80** **81** **82** **83** **84** **85** **86** **87** **88** **89** **90** **91** **92** **93** **94** **95** **96** **97** **98** **99** **100** **101** **102** **103** **104** **105** **106** **107** **108** **109** **110** **111** **112** **113** **114** **115** **116** **117** **118** **119** **120** **121** **122** **123** **124** **125** **126** **127** **128** **129** **130** **131** **132** **133** **134** **135** **136** **137** **138** **139** **140** **141** **142** **143** **144** **145** **146** **147** **148** **149** **150** **151** **152** **153** **154** **155** **156** **157** **158** **159** **160** **161** **162** **163** **164** **165** **166** **167** **168** **169** **170** **171** **172** **173** **174** **175** **176** **177** **178** **179** **180** **181** **182** **183** **184** **185** **186** **187** **188** **189** **190** **191** **192** **193** **194** **195** **196** **197** **198** **199** **200** **201** **202** **203** **204** **205** **206** **207** **208** **209** **210** **211** **212** **213** **214** **215** **216** **217** **218** **219** **220** **221** **222** **223** **224** **225** **226** **227** **228** **229** **230** **231** **232** **233** **234** **235** **236** **237** **238** **239** **240** **241** **242** **243** **244** **245** **246** **247** **248** **249** **250** **251** **252** **253** **254** **255** **256** **257** **258** **259** **260** **261** **262** **263** **264** **265** **266** **267** **268** **269** **270** **271** **272** **273** **274** **275** **276** **277** **278** **279** **280** **281** **282** **283** **284** **285** **286** **287** **288** **289** **290** **291** **292** **293** **294** **295** **296** **297** **298** **299** **300** **301** **302** **303** **304** **305** **306** **307** **308** **309** **310** **311** **312** **313** **314** **315** **316** **317** **318** **319** **320** **321** **322** **323** **324** **325** **326** **327** **328** **329** **330** **331** **332** **333** **334** **335** **336** **337** **338** **339** **340** **341** **342** **343** **344** **345** **346** **347** **348** **349** **350** **351** **352** **353** **354** **355** **356** **357** **358** **359** **360** **361** **362** **363** **364** **365** **366** **367** **368** **369** **370** **371** **372** **373** **374** **375** **376** **377** **378** **379** **380** **381** **382** **383** **384** **385** **386** **387** **388** **389** **390** **391** **392** **393** **394** **395** **396** **397** **398** **399** **400** **401** **402** **403** **404** **405** **406** **407** **408** **409** **410** **411** **412** **413** **414** **415** **416** **417** **418** **419** **420** **421** **422** **423** **424** **425** **426** **427** **428** **429** **430** **431** **432** **433** **434** **435** **436** **437** **438** **439** **440** **441** **442** **443** **444** **445** **446** **447** **448** **449** **450** **451** **452** **453** **454** **455** **456** **457** **458** **459** **460** **461** **462** **463** **464** **465** **466** **467** **468** **469** **470** **471** **472** **473** **474** **475** **476** **477** **478** **479** **480** **481** **482** **483** **484** **485** **486** **487** **488** **489** **490** **491** **492** **493** **494** **495** **496** **497** **498** **499** **500** **501** **502** **503** **504** **505** **506** **507** **508** **509** **510** **511** **512** **513** **514** **515** **516** **517** **518** **519** **520** **521** **522** **523** **524** **525** **526** **527** **528** **529** **530** **531** **532** **533** **534** **535** **536** **537** **538** **539** **540** **541** **542** **543** **544** **545** **546** **547** **548** **549** **550** **551** **552** **553** **554** **555** **556** **557** **558** **559** **560** **561** **562** **563** **564** **565** **566** **567** **568** **569** **570** **571** **572** **573** **574** **575** **576** **577** **578** **579** **580** **581** **582** **583** **584** **585** **586** **587** **588** **589** **590** **591** **592** **593** **594** **595** **596** **597** **598** **599** **600** **601** **602** **603** **604** **605** **606** **607** **608** **609** **610** **611** **612** **613** **614** **615** **616** **617** **618** **619** **620** **621** **622** **623** **624** **625** **626** **627** **628** **629** **630** **631** **632** **633** **634** **635** **636** **637** **638** **639** **640** **641** **642** **643** **644** **645** **646** **647** **648** **649** **650** **651** **652** **653** **654** **655** **656** **657** **658** **659** **660** **661** **662** **663** **664** **665** **666** **667** **668** **669** **670** **671** **672** **673** **674** **675** **676** **677** **678** **679** **680** **681** **682** **683** **684** **685** **686** **687** **688** **689** **690** **691** **692** **693** **694** **695** **696** **697** **698** **699** **700** **701** **702** **703** **704** **705** **706** **707** **708** **709** **710** **711** **712** **713** **714** **715** **716** **717** **718** **719** **720** **721** **722** **723** **724** **725** **726** **727** **728** **729** **730** **731** **732** **733** **734** **735** **736** **737** **738** **739** **740** **741** **742** **743** **744** **745** **746** **747** **748** **749** **750** **751** **752** **753** **754** **755** **756** **757** **758** **759** **760** **761** **762** **763** **764** **765** **766** **767** **768** **769** **770** **771** **772** **773** **774** **775** **776** **777** **778** **779** **780** **781** **782** **783** **784** **785** **786** **787** **788** **789** **790** **791** **792** **793** **794** **795** **796** **797** **798** **799** **800** **801** **802** **803** **804** **805** **806** **807** **808** **809** **8010** **8011** **8012** **8013** **8014** **8015** **8016** **8017** **8018** **8019** **8020** **8021** **8022** **8023** **8024** **8025** **8026** **8027** **8028** **8029** **8030** **8031** **8032** **8033** **8034** **8035** **8036** **8037** **8038** **8039** **8040** **8041** **8042** **8043** **8044** **8045** **8046** **8047** **8048** **8049** **8050** **8051** **8052** **8053** **8054** **8055** **8056** **8057** **8058** **8059** **8060** **8061** **8062** **8063** **8064** **8065** **8066** **8067** **8068** **8069** **8070** **8071** **8072** **8073** **8074** **8075** **8076** **8077** **8078** **8079** **8080** **8081** **8082** **8083** **8084** **8085** **8086** **8087** **8088** **8089** **8090** **8091** **8092** **8093** **8094** **8095** **8096** **8097** **8098** **8099** **80100** **80101** **80102** **80103** **80104** **80105** **80106** **80107** **80108** **80109** **80110** **80111** **80112** **80113** **80114** **80115** **80116** **80117** **80118** **80119** **80120** **80121** **80122** **80123** **80124** **80125** **80126** **80127** **80128** **80129** **80130** **80131** **80132** **80133** **80134** **80135** **80136** **80137** **80138** **80139** **80140** **80141** **80142** **80143** **80144** **80145** **80146** **80147** **80148** **80149** **80150** **80151** **80152** **80153** **80154** **80155** **80156** **80157** **80158** **80159** **80160** **80161** **80162** **80163** **80164** **80165** **80166** **80167** **80168** **80169** **80170** **80171** **80172** **80173** **80174** **80175** **80176** **80177** **80178** **80179** **80180** **80181** **80182** **80183** **80184** **80185** **80186** **80187** **80188** **80189** **80190** **80191** **80192** **80193** **80194** **80195** **80196** **80197** **80198** **80199** **80200** **80201** **80202** **80203** **80204** **80205** **80206** **80207** **80208** **80209** **80210** **80211** **80212** **80213** **80214** **80215** **80216** **80217** **80218** **80219** **80220** **80221** **80222** **80223** **80224** **80225** **80226** **80227** **80228** **80229** **80230** **80231** **80232** **80233** **80234** **80235** **80236** **80237** **80238** **80239** **80240** **80241** **80242** **80243** **80244** **80245** **80246** **80247** **80248** **80249** **80250** **80251** **80252** **80253** **80254** **80255** **80256** **80257** **80258** **80259** **80260** **80261** **80262** **80263** **80264** **80265** **80266** **80267** **80268** **80269** **80270** **80271** **80272** **80273** **80274** **80275** **80276** **80277** **80278** **80279** **80280** **80281** **80282** **80283** **80284** **80285** **80286** **80287** **80288** **80289** **80290** **80291** **80292** **80293** **80294** **80295** **80296** **80297** **80298** **80299** **80300** **80301** **80302** **80303** **80304** **80305** **80306** **80307** **80308** **80309** **80310** **80311** **80312** **80313** **80314** **80315** **80316** **80317** **80318** **80319** **80320** **80321** **80322** **80323** **80324** **80325** **80326** **80327** **80328** **80329** **80330** **80331** **80332** **80333** **80334** **80335** **80336** **80337** **80338** **80339** **80340** **80341** **80342** **80343** **80344** **80345** **80346** **80347** **80348** **80349** **80350** **80351** **80352** **80353** **80354** **80355** **80356** **80357** **80358** **80359** **80360** **80361** **80362** **80363** **80364** **80365** **80366** **80367** **80368** **80369** **80370** **80371** **80372** **80373** **80374** **80375** **80376** **80377** **80378** **80379** **80380** **80381** **80382** **80383** **80384** **80385** **80386** **80387** **80388** **80389** **80390** **80391** **80392** **80393** **80394** **80395** **80396** **80397** **80398** **80399** **80400** **80401** **80402** **80403** **80404** **80405** **80406** **80407** **80408** **80409** **80410** **80411** **80412** **80413** **80414** **80415** **80416** **80417** **80418** **80419** **80420** **80421** **80422** **80423** **80424** **80425** **80426** **80427** **80428** **80429** **80430** **80431** **80432** **80433** **80434** **80435** **80436** **80437** **80438** **80439** **80440** **80441** **80442** **80443** **80444** **80445** **80446** **80447** **80448** **80449** **80450** **80451** **80452** **80453** **80454** **80455** **80456** **80457** **80458** **80459** **80460** **80461** **80462** **80463** **80464** **80465** **80466** **80467** **80468** **80469** **80470** **80471** **80472** **80473** **80474** **80475** **80476** **80477** **80478** **80479** **80480** **80481** **80482** **80483** **80484** **80485** **80486** **80487** **80488** **8**

A large black rectangular redaction box covers the majority of the page content, starting below the header and ending above the footer. It is positioned on the left side of the page, with a thin vertical black bar extending from the top edge of the redaction area down to the bottom edge.

ANSWER

11. **What is the primary purpose of the *Journal of Clinical Endocrinology and Metabolism*?**

111

